Electromagnetic stimulation of the pelvic floor with the Emsella device is a FDA 510(k) approved therapy whereby a coil generates pulsed electromagnetic fields that penetrate deep into the pelvic floor muscles inducing stimulation and providing rehabilitation of weak pelvic muscles. It was first described as a conservative treatment for stress urinary incontinence (SUI) in 1999 and demonstrated encouraging results [28]. The Emsella Chair is a novel high intensity focused electromagnetic (HIFEM) technology, currently used for the treatment of SUI, in addition to other pelvic floor related disorders. The program phases consist of an intense awakening of the deconditioned pelvic floor muscles (cat), stimulation, and relaxation. The repetition of the phases and focused electromagnetic energy delivery leads to pelvic floor stimulation, adaptation, and remodeling. Alternative settings of pulse strength and frequency could theoretically be used to

stimulate the PFM without inducing muscular contraction. This could induce fatigue in muscle groups, leading to muscle relaxation & reduced hypertonic pelvic floor dysfunction in a manner similar manner to PFPT.

This technology is typically not covered by insurance, is minimally invasive, and safe, but has limited data available. Currently, there is no data available evaluating efficacy of this technology for CPP. The purpose of this study is to compare the Emsella Chair to sham and to determine whether electromagnetic technology is effective in the treatment of CPP.

OBJECTIVES AND ENDPOINTS

Primary Objective - Efficacy

The primary objective of this study is to compare the efficacy of Emsella Chair to sham by evaluating the change in subject-reported pain and discomfort as measured by the Visual Analog Scale (VAS). Mean change in VAS from baseline to end of treatment will be compared between the Emsella Chair group and the sham group.

Hypothesis: Subjects in the Emsella Chair group will show a greater decrease in pain, as measured by VAS, compared to subjects in the sham group.

Secondary Objectives - Efficacy

The secondary efficacy objectives in this study are to compare the Emsella Chair versus sham in relation to several different domains (pain, urinary symptoms, sexual function, quality of life) using validated questionnaires.

- Change in subject-reported impression of CPP severity as measured by the Patient Global Impression of Severity scale (PGI-S)

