For treatment delivery, subjects will be asked to sit on the device and the height will be adjusted until the subject's feet are on the floor. The active treatments are individualized, since some subjects will be more sensitive than others, and thresholds may vary from visit to visit. The Emsella Chair will be turned on and the setting gradually increased to the subject's sensory threshold; the maximum sensation the subject can tolerate, with the goal of a minimum 50% setting. The subject will not be left unattended throughout the treatment session. The treatment threshold should be increased with every treatment until the subject reaches 100%.

Sham subjects will be positioned on the device in the same manner. The sham treatment will provide some sensation without active HIFEM technology. The programming for the sham treatment will have an amplitude limitation, with the setting below therapeutic level (<10% power).

Regardless of group assignment, each treatment is \leq approximately 28 minutes at which time the device automatically shuts off. If at any time point, there are two treatment visits where the subject cannot tolerate a setting of at least 50%, they will be withdrawn from the study at the second occurrence. If a subject cannot endure the entire treatment duration, they will be withdrawn from the study.

The primary endpoint for follow up evaluation will be 4 weeks after completion of the last treatment (week 8 of the study). The durability endpoint is 4 weeks following the primary endpoint (week 12 of the study).

At each clinic visit, study procedures will be performed as specified in the table of events, located in Appendix A.

Study subjects will not be compensated for their participation in the trial. However, all research related activities, specified on the table of events, will be provided at no cost to the study subject.

TREATMENT ALGORITHM

Emsella Chair (2 times/week for 4 weeks)	Sham Emsella (2 times/week for 4 weeks)
--	---

Treatment Group Assignment

Subjects meeting all eligibility criteria will be randomized to the active treatment group or sham in a 1:1 ratio.

RANDOMIZATION and BLINDING

The study will be performed in a single-blind manner (subject and biostatistician will be blinded to treatment). Subjects will be randomized 1:1 to active Emsella Chair treatment or sham treatment. Subjects will be enrolled in the study and randomized:

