Visit 10, Week 12, Secondary Endpoint

Approximately 8 weeks after finishing treatment, the subject will return to the study site for a clinic visit. The subject will complete the VAS, PGI-I, PGI-S, FSFI (females only) or BSFI (males only), BDI, OAB-q, ICSI-PI, GAD7, MPQ, PCS, and GRA. Concomitant medications and adverse events will be reviewed and changes from the previous visit will be recorded.

After completing all visit activities, the subject will be unblinded to treatment group. If subjects were in the sham group, they will be offered the opportunity to receive Emsella Chair treatments. Subjects choosing to continue in the study will follow the same active treatment protocol and follow the schedule of activities for Visits 1-10, specified in Appendix A.

SUBJECT DISCONTINUATION OR WITHDRAWAL

Subjects are free to discontinue study participation at any time upon request. Subjects who discontinue study treatment or active participation in the study will no longer receive treatment with Emsella Chair or sham. When a subject withdraws from the study, the reason(s) for withdrawal shall be recorded. Every effort will be made to obtain all end-of-treatment measures.

Additionally, subjects may be withdrawn from the study by the Principal Investigator (PI) for any of the following reasons:

- Subject cannot complete the full duration of treatment
- Subject cannot tolerate a minimum treatment level of 50% at any two treatment visits
- Development of any condition or AE that are clinically significant and may pose an additional risk to the subject
- The PI decides is in the best interest of the subject to withdraw from the study
- Subject is unable to follow Investigators' instructions and/or to comply with the study protocol

Replacements

Subjects who have been randomly assigned to receive treatment and who subsequently discontinue prematurely from the study may be replaced by another subject. The goal is to have 60 patients complete the entire study; 30 patients in each arm. Therefore, if/when subjects withdraw from the study prior to completing visit 9, an additional subject will be enrolled. Each subject will be assigned their own unique study identification number.

Subjects who fail to satisfy inclusion and exclusion criteria at screening may be rescreened at the discretion of the PI.

TABLE OF EVENTS

The table of events is included in Appendix A.

RISKS AND BENEFITS

Possible Risks

- Worsening of CPP
- Muscular pain
- Temporary muscle spasm

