We evaluated the difference in VAS decrease (primary outcome) between the Emsella Chair group and the Sham group that would be detectable with 80% power and assuming a 5% significance level. We used Pass 16 to determine the effect size detectable when testing for the between-group difference in the post-pre difference in a score. We assumed that the standard deviation of VAS would be 2.5 cm both at baseline and at visit 9. We varied the within-subject correlation between pre- and post-scores from 0.1 to 0.8. This correlation describes the extent to which subjects show similar post-pre differences, with a correlation of 0.2 being observed when there is relatively little similarity in subjects' post-pre differences. Based on these assumptions, we would have 80% power to detect a difference of 2.3 cm between the decrease in VAS in the Emsella Chair group and the Sham group, given a sample size of 30 subjects per arm and a within-subject correlation of 0.2. In this scenario, we could detect a 3.3 cm decrease in VAS in the Emsella chair group if the Sham group shows a 1.0 cm decrease in VAS. The difference in the VAS decrease detectable decreases as the within-subject correlation increases (Figure 2).

[figure not shown]

Figure 2 – The difference in the decrease in VAS between the Emsella Chair and Sham groups detectable with a total sample size of 60.

Analysis Sets

Data analysis will be performed on a full analysis set (FAS), a per protocol set (PPS), an intent-to-treat (ITT) set, a durability set (DS), and a safety analysis (SA) set.

The FAS will be used for the primary analysis. The FAS will consist of all randomized subjects who receive at least one treatment session and have at least 1 post baseline primary efficacy assessment (VAS score). All analyses using the FAS will group participants according to randomized treatment.

The PPS will be used for a supportive analysis and will be defined as all subjects included in the FAS who do not have any significant protocol deviations. All analyses using the PPS will group subjects according to the actual treatment received.

The ITT set will consist of all randomized subjects who receive at least one treatment session. All analyses using the ITT set will group subjects according to randomized treatment. Subjects who do not have any post-baseline assessments will be treated as non-responders for ITT analyses.

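### Subjects who cannot tolerate 50% power or a full session leave the study, not just treatment, with no Week 8 or Week 12 VAS scheduled; the 50% rule can act only in the active arm

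*Combined protocol and SAP*

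**What the plan says.** **Tolerance rules (Methodology).** Active treatment is raised to the most the subject can tolerate, aiming for a setting of 50% or more. If "there are two treatment visits where the subject cannot tolerate a setting of at least 50%, they will be withdrawn from the study"; this takes effect on the second such visit. A second rule has the same consequence: "If a subject cannot endure the entire treatment duration, they will be withdrawn from the study". Sham programming is limited to less than 10% power.

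**Withdrawal (Subject Discontinuation or Withdrawal).** The same two reasons reappear in a list headed by the statement that "subjects may be withdrawn from the study by the Principal Investigator (PI) for any of the following reasons", so what is mandatory in one section is discretionary in the other. For data after withdrawal the section says only: "Every effort will be made to obtain all end-of-treatment measures".

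**What end of treatment means.** The Primary Objective states: "Mean change in VAS from baseline to end of treatment will be compared". The Endpoints and Methodology sections place the primary endpoint 4 weeks after the last treatment, at Week 8 (Visit 9), and the durability endpoint at Week 12 (Visit 10).

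**Replacement (Replacements).** The target is 30 completers per arm, and "if/when subjects withdraw from the study prior to completing visit 9, an additional subject will be enrolled".

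**Analysis Sets and Missing Data.**
- The FAS, used for the primary analysis, needs one session and one post-baseline VAS, and analyzes by randomized arm.
- The ITT non-responder rule covers only subjects with no post-baseline assessment at all.
- The durability set needs all eight treatments and the Week 12 visit.
- Below 5% missing, efficacy analyses are complete case. Above 5%, dropout is compared between arms and against baseline VAS, and multiple imputation follows unless there is evidence that data are missing not at random.

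**The concern.** Whether a subject can tolerate 50% is learned after randomization and only on active treatment. Read literally, the rule would withdraw every sham subject at the second visit, because none is ever taken near 50%; that cannot be intended. Read sensibly, it filters the active arm by tolerance and leaves the sham arm unfiltered. The full-session rule can act in both arms, though it is plausibly met more often under active stimulation.

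Stopping treatment for intolerance is reasonable. The difficulty is that the subject leaves the study as well, so the primary outcome is lost for a reason caused by the treatment. If subjects who tolerate stimulation poorly also have worse pain at Week 8, the remaining active subjects look better than the randomized arm really is. The protocol's list of possible risks includes worsening pelvic pain and muscle spasm, which makes this plausible, but nothing in the documents shows it.

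**Working it through.** **1. Does anything in the plan supply a Week 8 or Week 12 value for these subjects?**

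| Provision | What it does | Supplies the value? |
|---|---|---|
| Best-effort sentence on withdrawal | Can be read as the last session or as Week 8; names no week | Not reliably for Week 8; nothing for Week 12 |
| FAS membership through a post-session VAS | Keeps the subject in the randomized arm | No |
| ITT non-responder rule | Applies only with no post-baseline assessment | No; anyone with a post-session VAS falls outside it |
| Replacement | Restores the number of completers | No |
| Durability set | Requires all eight treatments | No; excludes these subjects by definition |
| Imputation above 5% missing | Models the missing value | Not an observed value |

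Neither the visit descriptions nor Appendix A, as far as it can be read, schedules Visit 9 or 10 for a withdrawn subject.

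**2. Reproduce the plan's figure.** Inputs from Sample Size Calculation: SD 2.5 cm at both times, correlation 0.2, 30 per arm, 5% significance (taken as two-sided), 80% power.
- SD of change = 2.5 × √(2 × (1 − 0.2)) = 3.162 cm
- SE of the difference in change = 3.162 × √(2/30) = 0.816 cm
- Detectable difference = (1.960 + 0.842) × 0.816 = 2.29 cm, matching the stated 2.3 cm. A one-sided test would give 2.03 cm, which does not match.

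**3. Size of the bias.** The documents give neither a withdrawal rate nor an outcome for those withdrawn, so the following are assumptions:
- all k withdrawals are active subjects
- replacement brings each arm to 30 completers, and no one else is missing
- missingness is counted per subject
- the withdrawn would have improved d = 1 to 2 cm less than those who stay

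Then missing share = k/(60 + k); withdrawn share of the active arm p = k/(30 + k); completer-only bias = p × d.

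| k | Missing | Route in the plan | p | Bias, d = 1 to 2 cm |
|---|---|---|---|---|
| 3 | 3/63 = 4.8% | Complete case | 3/33 = 0.091 | 0.09 to 0.18 cm |
| 4 | 4/64 = 6.25% | Imputation | 4/34 = 0.118 | at most 0.12 to 0.24 cm |
| 6 | 6/66 = 9.1% | Imputation | 6/36 = 0.167 | at most 0.17 to 0.33 cm |

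The imputation rows are maxima, reached if imputation recovers none of the difference. If it recovers half, they halve: 0.06 to 0.12 cm for k = 4 and 0.08 to 0.17 cm for k = 6.

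**4. Type I error on the complete-case route (k = 3).** Bias/SE = 0.091/0.816 = 0.11 to 0.182/0.816 = 0.22. With shift δ, the two-sided error is Φ(−1.96 + δ) + Φ(−1.96 − δ), which gives 5.1% to 5.6%.

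**5. A more extreme case.** If 20% of the active arm is withdrawn and d = 2 cm, completer-only bias is 0.20 × 2 = 0.40 cm and the type I error 7.7% (noncentral t, 30 completers per arm). Reaching 30 active completers would then take 38 randomized, so 8/68 = 11.8% would be missing. The plan would be on the imputation route, and these figures are an upper limit, not an expectation.

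**The case against.** The strongest reply has four parts.

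- **The best-effort sentence may already reach Week 8.** The Primary Objective uses end of treatment for the primary contrast, and the Endpoints section puts that contrast at Week 8. This reading is fair, and for Week 8 part of the defect is unclear wording. It does not help Week 12, and an ambiguous best effort is weaker than a scheduled visit.
- **The complete-case route is narrow.** It allows at most 3 missing of 63 from all causes, so ordinary dropout would soon push the trial over 5%, where dropout by arm is examined and imputation used. This stands and limits the damage. Observed data cannot, however, exclude that values are missing not at random, so imputation reduces the bias without ensuring its removal.
- **Imputation would have something to work with.** The 50% rule cannot trigger before a second treatment visit, so these subjects normally have baseline VAS and pre- and post-session scores. This stands too, but scores around one or two early sessions are not the pain level 4 weeks after treatment.
- **Some parts are minor.** The mandatory and discretionary wordings are an editorial conflict. Replacements are already described as additional subjects, and the FAS keeps all randomized subjects who meet its criteria, so no change is needed there. Durability among those who completed treatment is a legitimate, narrower question.

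None of these secures an observed Week 8 or Week 12 value for the subjects concerned.

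**Conclusion.** The concern holds and should be fixed. As written, the tolerance rules cause avoidable, largely one-arm loss of the primary endpoint, and the 50% rule has no workable meaning for sham. The likely effect is modest: 0.09 to 0.18 cm and a type I error of 5.1 to 5.6% on the complete-case route with three withdrawals, and at most 0.33 cm with six, against a detectable 2.3 cm. These figures depend on the assumed withdrawal numbers, on all withdrawals being active, and on a Week 8 change 1 to 2 cm worse in those withdrawn. If they do no worse the bias is zero; if they do better its sign reverses. The case for changing the plan rests on the low cost of preventing the loss more than on the size of the expected bias.

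**What to change.** 1. Make both tolerance rules reasons to stop study treatment only. These subjects attend Visits 9 and 10 as already designed and complete the VAS and questionnaires. Name the Week 8 and Week 12 VAS in the best-effort sentence, and align the mandatory and discretionary wording of the two sections.
2. State how the 50% rule applies to sham subjects. No view is offered here on which setting should count.
3. Run the Week 12 durability comparison on the FAS, with the durability set as supportive.

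**Cost:** protocol wording, plus two existing visits for the few subjects who stop treatment, some of whom may decline. There are no new procedures and no change in sample size. The estimated effect may come out slightly smaller, because subjects who did not tolerate the device would count at their observed outcome.

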- After all screening activities have occurred and it has been determined that the subject meets all inclusion criteria without the presence of exclusionary criteria.
- After the subject agrees to enroll and comply with the study protocol, regardless of study group assignment.

The process of randomization will be as follows:

- Randomization will be performed using a computer-based random number generator. Randomization envelopes will be provided by the study's biostatistician and will be securely stored in a locked cabinet.
- Delegated study staff will solely be responsible for opening the randomization envelopes and delivering the study treatments, according to the group assignment. Ultimately, they will be responsible for maintaining the confidentiality and security of the randomization envelopes and the Subject and Enrollment and Randomization Log.
- After the participant is randomized, the delegated study staff will complete the *Subject Enrollment and Randomization Log*. The study the log will be stored in the regulatory binder.
- The biostatistician will prepare more envelopes, if necessary.

Breaking the Blind

A subject's treatment assignment will not be broken until the end of the study unless medical treatment of the subject is dependent on knowing the study treatment the subject received. If the blind needs to be broken because of a medical emergency, the investigator may unblind an individual subject's treatment allocation.

STUDY ASSESSMENTS AND PROCEDURES

Screening: Visit 0

Before performing any research activities, the study will be explained in detail and adequate time will be allowed for answering questions. If the subject decides to pursue study participation, they will sign the institutional review board (IRB)-approved informed consent document.

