Once informed consent is obtained, a study identification number will be assigned. A detailed interview will be conducted, including demographics, medical history, past surgical, gynecological and obstetric history (if applicable), and concomitant medications. Subjects will complete a baseline visual analog pain scale. Weight will be measured. Females will undergo a gynecologic pelvic examination, which includes assessment of levator muscle tenderness. For male subjects, a digital rectal examination will be performed to assess levator muscle tenderness. A dipstick urinalysis will be performed. If positive for leukocytes, a urine culture will be sent. If a subject has a confirmed symptomatic urinary tract infection

(UTI) per investigator's clinical judgment, they will be deferred from screening until treatment is completed and may resume once symptoms resolve. If the female subject is of child-bearing potential, a urine pregnancy test will be performed. If the urine pregnancy test is positive, the subject will be ineligible for study participation. Subjects will complete self-administered questionnaires (PGI-S, FSFI or BSF, BDI, OAB-q, ICSI-PI, GAD 7, MPQ, PCS). Adverse events will be assessed at each study visit including the screening visit. Screening activities may be completed at Visit 1, prior to randomization, if needed. Data collected prior to randomization will be considered baseline.

Study Visit 1: Week 1

A urine pregnancy test (if applicable) will be performed. If the urine pregnancy test is positive, the subject will be ineligible for study participation. Additionally, any screening activities that were not completed at the initial visit will be conducted. After all screening activities are completed, and it is determined that the subject meets the eligibility criteria, the subject will be enrolled in the study and randomized to one of the two intervention arms. The first treatment will be conducted at this visit.

The subject will complete VAS before and after treatment. Concomitant medications and adverse events will be reviewed and changes from the previous visit will be recorded.

If at any time a patient reports a fever, an oral temperature will be obtained. If a fever, defined as $\geq 38^{\circ}$ Celsius, is present, treatment will be delayed until the fever is resolved at a later visit.

Study Treatments: Visit 2-Visit 8

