A database will be created utilizing RedCap or MS Excel software. Only designated study personnel will have access to the database, which will be stored on the Urology Research Department's shared drive. Access to the computerized system will be password protected. To ensure accuracy of data entry, database entries will be cross-checked against source documents. The shared drive is backed up nightly to ensure minimal data loss, even in the most catastrophic system failure. The database will be active until all study visits are completed, final monitoring activities have been conducted, and all data queries have been resolved. After that time, the database will be locked, prohibiting any changes to the data.

All study records, including both paper and electronic, will be stored in accordance with all federal and institutional requirements, including, but not limited to, the HIPAA Privacy Rule, the Food and Drug Act, and Medicare policy. The stored data will be kept in a secure, protected manner. All records will be retained, at a minimum, for eleven years beyond study completion.

SUMMARY of EXISTING STUDY DATA

The BTL Emsella has received 510(k) approval as a "nonimplanted electrical continence device" and is currently being used as a non-invasive treatment for SUI. The limited number of studies on this HIFEM technology have focused on its effects on stress, urge, and mixed urinary incontinence as well as quality of life. A white paper, entitled "HIFEM™ Technology Can Improve Quality of Life of Incontinent Patients" summarizes the results of a pilot study, which enrolled and treated 30 women with stress, urge or mixed urge incontinence [29]. Quality of life (QOL) was assessed after the women received 6 treatments, and again at 3 and 6 months post treatment. Ninety-five percent (95%) of the women reported improvement in QOL after treatment completion. Results were maintained over the follow-up periods. Additionally, 67% of the women decreased or eliminated the use of incontinence pads. Similar results were seen in studies by Samuels, Alinsod, Cidranes and Blanco [30, 31, 32, 33]. Additionally, advance ultrasound (elastography) revealed elastographic changes, indicating the improvement in pelvic muscle tone in all the subject's post-treatment.

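### Allocation concealment is not assured: the unblinded staff who treat also keep the envelopes, open them and hold the log, so selection bias is possible, though not shown

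*Combined protocol and SAP*

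**What the plan says.** RANDOMIZATION and BLINDING limits blinding to two parties: "The study will be performed in a single-blind manner (subject and biostatistician will be blinded to treatment". The treating staff therefore know each assignment once it is made.

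On the sequence, the plan says only: "Randomization will be performed using a computer-based random number generator". It does not say whether randomization is simple or restricted, and gives no block size. On storage: "Randomization envelopes will be provided by the study's biostatistician and will be securely stored in a locked cabinet".

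On custody and use: "Delegated study staff will solely be responsible for opening the randomization envelopes and delivering the study treatments, according to the group assignment". It adds that "they will be responsible for maintaining the confidentiality and security of the randomization envelopes and the Subject and Enrollment and Randomization Log". These staff also fill in the log after each randomization.

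Randomization must follow confirmed eligibility and the subject's agreement to take part in either group. Under Screening: Visit 0, "Screening activities may be completed at Visit 1, prior to randomization, if needed", and Visit 1 is also the visit of randomization and first treatment. Under Replacements, subjects who fail screening "may be rescreened at the discretion of the PI". METHODOLOGY places all study activities in one Urology Research office, with treatment given by that office's delegated staff.

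**The concern.** Concealment means that whoever decides whether and when a subject enters cannot know or predict the next assignment. Here the locked cabinet is in the charge of unblinded trial staff, who also see every past assignment in the log. No independent holder is named, and no section keeps these staff apart from those who screen.

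Entry involves judgement: likely compliance (inclusion criterion 1), the investigator's opinion (exclusion criterion 13) and rescreening at the PI's discretion. If knowledge or a guess of the next assignment reached those decisions, subjects expected to improve could be entered preferentially when the next assignment was active.

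The planned analysis could not remove the resulting difference. The primary model contains group, time, their interaction and subject. Subject effects absorb the level of pain, not a difference in expected change, and expected change is what steering would alter. The outcome is also self-rated.

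**Working it through.** **1. The plan's own figure.** Inputs from Sample Size Calculation: SD 2.5 cm at both times, within-subject correlation 0.2, 30 per arm, 80% power, 5% level (two-sided assumed).
- SD of change = 2.5 × √(2 × (1 − 0.2)) = 3.16 cm.
- SE of the between-arm difference = 3.16 × √(2/30) = 0.816 cm.
- Detectable difference = 0.816 × (1.96 + 0.84) = 2.29 cm, or 2.33 cm with the t distribution. The plan's 2.3 cm is reproduced, so 0.816 cm is a fair scale for any bias.

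**2. How predictable is the next assignment from the log?** The method is not stated, so this is a range of assumptions. Someone who sees all past assignments and knows the scheme does best by guessing the arm with more places left. For a balanced block of 2n, the expected proportion correct is g = [n + (2^(2n)/C(2n,n) − 1)/2]/(2n). Under simple randomization past assignments carry no information, so g = 0.50. If envelopes are read early, g = 1.

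**3. What would that do to the result?** Suppose a fraction f of entries is steered, and subjects chosen for active differ from those chosen for sham by d in expected VAS change. With guesses correct at rate g, the shift in the between-arm difference is f × d × (2g − 1). Two-sided type I error is P(|Z + shift/0.816| > 1.96). Take f = 0.20 and d = 2.5 cm, so f × d = 0.5 cm. Neither value comes from the documents.

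| Sequence or situation | g | Shift (cm) | Type I error |
|---|---|---|---|
| Simple randomization | 50% | 0 | 5.0% |
| One list forced to 30/30 | 57% | 0.07 | 5.1% |
| Fixed blocks of 6 | 68% | 0.18 | 5.6% |
| Fixed blocks of 4 | 71% | 0.21 | 5.7% |
| Fixed blocks of 2 | 75% | 0.25 | 6.1% |
| Envelopes read early | 100% | 0.50 | 9.4% |

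**4. Sensitivity to the assumptions.**
- With d = 1 cm and f = 0.20, blocks of 4 give 5.1% and envelopes read early give 5.7%.
- If every entry were steered by ±0.5 cm (f = 1, d = 1 cm, t distribution), the figures are 5.0% (simple), 5.4% (30/30 list), 7.3% (blocks of 6), 7.9% (blocks of 4) and 22.6% (read early).
- The table applies the average guess rate, as if steered entries were spread over the sequence. Someone who knew a fixed block size and acted only on forced assignments at block ends would be certain there: on average 15 of 60 for blocks of 6 and 20 of 60 for blocks of 4. Those entries would behave like the last row. This needs a further assumption about conduct, but it is a reason to vary block sizes and withhold them.

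**The case against.** Much of the opposing case stands.

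- **Seeing the next assignment rests on silence.** Nothing says that envelopes can be read or opened early. The biostatistician supplies them, and the staff are charged with their confidentiality. That sealing, opacity and numbering are not mentioned may be only a gap in description, and reading ahead would require misconduct or defective envelopes.
- **Guessing needs a restricted list.** A reader might infer restriction from the 30-per-arm target, since 60 simple draws give exactly 30/30 with probability 0.103. The documents do not support that step. Thirty per arm is a goal for completers, pursued by replacing withdrawals; enrolment is approximate, and further envelopes may be prepared. Simple randomization fits this text.
- **The link to entry decisions is not shown.** The discretion cited belongs to the investigator and the PI, and no section says that the envelope staff screen. Provision for the investigator to unblind in an emergency suggests that investigators do not routinely know assignments.
- **There is some oversight.** The first subject is monitored after Visit 1, and a nurse not directly involved audits at three points. Envelope reconciliation is not among the listed checks.

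What remains is custody. This is a stated arrangement, not merely missing detail: one unblinded group stores, opens, treats and logs. Randomizing after eligibility fixes the order of steps, but it does not hide the next assignment while eligibility is being judged.

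**Conclusion.** The point holds as a gap in allocation concealment. Selection bias is possible because custody is not separated from treatment, and nothing separates the custodians from screening and entry. It is not shown to occur or to be likely.

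Under the assumed 20% steering and 2.5 cm difference, with the average guess rate, inflation from the log alone runs from none (simple randomization) to 6.1% (blocks of 2). A reader might take 0.5 cm and 9.4% as the expected damage. Those figures require the steered assignments to be known with certainty, which in this model means envelopes read early, and no section says that this can happen. Nor should the 1.0 cm sham decrease in the sample size section be read as a predicted sham response; it is an illustrative scenario. The plan's sample size and power figures are unaffected.

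This is a cheap improvement, worth making before enrolment because concealment cannot be restored afterwards.

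**What to change.** In RANDOMIZATION and BLINDING, replace the site-held envelopes with a concealed electronic release of a 1:1 list. Use randomly varying block sizes that site staff do not know. Release each assignment only after consent, confirmed eligibility and baseline VAS have been entered and time-stamped. The REDCap randomization module is one candidate, if the site has it. The protocol names the software only as a database option: "A database will be created utilizing RedCap or MS Excel software".

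If envelopes are kept, require that they be sealed, opaque and sequentially numbered, and held by someone not involved in screening or treatment. The subject ID and date should be written on each before it is opened. Reconcile used and unused envelopes against the biostatistician's list at the audits already scheduled in the DATA and SAFETY MONITORING PLAN. State the sequence method as well, keeping the block sizes in a document that site staff do not see.

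The electronic route costs a wording change, a short set-up and staff access to the system at Visit 1. The envelope route needs an independent holder who is available when subjects are randomized. Neither adds patients or visits.
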